8. STATISTICAL METHODOLOGY AND STATISTICAL ANALYSES

8.1. Statistical Methods

As this is a descriptive study only, no formal hypothesis testing will be performed. *No pooled analyses across the two independent age cohorts are planned.*

8.2. Population Pharmacokinetic Analyses

Pantoprazole concentration data will be analyzed using a population PK analysis approach (nonlinear mixed-effects models). Prior pediatric PK data may be used to guide and assist the model building and covariate selection. A two-compartment model with IV infusion will be used to describe pantoprazole concentrations, with clearance (CL) and volume of distribution (Vd) of the central compartment being the key population PK parameters in the model. The potential influence of covariates, including age and body weight, on these parameters will be explored during the model building phase of the analysis. Other covariates, including gender and baseline values, may also be explored using graphical approaches.

The final population PK model will also be used to estimate the following PK Parameters: maximum plasma concentration (C_{max}), area under the plasma concentration time profile from time zero to the 24 hour time post dose (AUC_{24}), area under the plasma concentration time profile from time zero extrapolated to infinite time (AUC_{inf}) and terminal phase half life ($T_{1/2}$) of pantoprazole following single and multiple IV doses.

Box and whisker plots for individual subject parameters (AUC_{24} , AUC_{last} and C_{max}) be presented by cohort and dosing and overlaid with geometric means.

A Population Modeling Analysis Plan (PMAP-EQDD-B179a-sNDA-1153) describing the details of the model building, covariate assessment, model validation and PK parameter estimation will be provided separately.

Presentations for pantoprazole concentrations will include:

- A listing of all concentrations sorted by cohort (present in heading), subject id, day and nominal time postdose. The concentration listing will also include the actual times. Deviations from the nominal time will be given in a separate listing.
- A summary of concentrations by cohort, day and nominal time postdose, where the set of statistics will include n, mean, median, standard deviation, coefficient of variation (cv), minimum, maximum and the number of concentrations above the lower limit of quantification.
- Median concentrations time plots (on both linear and semi-log scales) against nominal time postdose by dosing (single dose (Day 1) and multiple dose (Days 2 & 7 combined) on the same plot per scale, based on the summary of concentrations by cohort, dosing (single dose and multiple dose) and time postdose).
- Mean concentrations time plots (on both linear and semi-log scales) against nominal time postdose by dosing (single dose (Day 1) and multiple dose (Days 2 & 7 combined) on the same plot per scale, based on the summary of concentrations by cohort, dosing (single dose and multiple dose) and time postdose).

- Individual concentration time plots by cohort and dosing (single dose and multiple dose) (on both linear and semi-log scales) against actual time postdose (there will be separate spaghetti plots for each cohort and dosing per scale).
- Individual concentration time plots by subject (on both linear and semi-log scales) against actual time postdose [there will be separate plots for each subject (containing both dosing (single dose and multiple dose)) per scale].

For summary statistics, median and mean plots by sampling time, the nominal PK sampling time will be used, for individual subject plots by time, the actual PK sampling time will be used.

8.3. Safety Analysis

A set of summary tables split by age cohort will be produced to evaluate any potential risk associated with the safety and toleration of administering pantoprazole.

8.3.1. Treatment and Disposition of Subjects

Subject evaluation groups will show end of study subject disposition and will show which subjects were analyzed for pharmacokinetics, as well as for safety (adverse events and laboratory data). Frequency counts will be supplied for subject discontinuation(s) by cohort.

Data will be reported in accordance with the sponsor reporting standards.

8.3.2. Demographic and Clinical Examination Data

A break down of demographic data will be provided for age, race, weight, body mass index, and height. Each will be summarized by sex at birth and 'All Subjects' in accordance with the sponsor reporting standards.

8.3.3. Discontinuation(s)

Subject discontinuations, temporary discontinuations or dose reductions due to adverse events will be detailed and summarized by cohort.

Data will be reported in accordance with the sponsor reporting standards.

8.3.4. Adverse Events

Adverse events will be reported in accordance with the sponsor reporting standards by cohort.

8.3.5. Laboratory Data

Laboratory data will be listed in accordance with the sponsor reporting standards.

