2.2.2. Secondary Endpoints

• PK Parameters to be estimated from the population PK model:

Maximum plasma concentration (Cmax), area under the plasma concentration-time profile from time zero to the 24 hour time post dose (AUC24), area under the plasma concentration-time profile from time zero extrapolated to infinite time (AUCinf) and terminal phase half-life (T1/2) of pantoprazole following single and multiple IV doses.

- Safety and tolerability of single- and multiple doses of IV pantoprazole sodium for each of the two age cohorts will be assessed by physical examinations, adverse event (AE) monitoring, clinical laboratory measurements, blood pressure, and pulse rate.
- CYP2C19 genotype to determine the presence of the gene for the major enzyme responsible for metabolism of pantoprazole.

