9.5. Safety Analysis

Adverse events, physical examinations, blood pressure, pulse rate, and safety laboratory data will be reviewed and summarized on an ongoing basis during the study to evaluate the safety of subjects. Any clinical laboratory, blood pressure, and pulse rate abnormalities of potential clinical concern will be described. Safety data will be presented in tabular and/or graphical format and summarized descriptively, where appropriate.

Safety results will be reported separately for each age cohort.

Safety summaries will be produced in accordance with Clinical Data Interchange Standards Consortium (CDISC) and Pfizer Standards (CaPS) for safety reporting.

Baseline characteristics (eg, demographics, medical history) will be also summarized using CaPS for reporting.

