6.2. Safety Endpoints

Any events occurring following start of treatment or increasing in severity will be counted as treatment emergent.

Events that occur in a non-treatment period (for example, Washout or Follow-up) will be counted as treatment emergent and attributed to the previous treatment taken.

The following data are considered in standard safety summaries (see protocol for collection days and list of parameters):

- adverse events,
- laboratory data,
- vital signs data.

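### SAP 8.3.5 plans only a listing of laboratory data, in conflict with SAP 6.2, the SAP 8.3 lead-in and Protocol 9.5

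*SAP*

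**What the plan says.** Protocol 2.2.2 has one safety and tolerability endpoint, which "will be assessed by physical examinations, adverse event (AE) monitoring, clinical laboratory measurements, blood pressure, and pulse rate". Protocol 9.5 then makes three statements that bear on laboratory data:

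- on review: "Adverse events, physical examinations, blood pressure, pulse rate, and safety laboratory data will be reviewed and summarized on an ongoing basis during the study";
- on abnormalities: "Any clinical laboratory, blood pressure, and pulse rate abnormalities of potential clinical concern will be described";
- on presentation: "Safety data will be presented in tabular and/or graphical format and summarized descriptively, where appropriate".

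SAP 6.2 introduces its list with "The following data are considered in standard safety summaries", and the list is adverse events, laboratory data and vital signs. The opening of SAP 8.3 promises a set of safety tables by age cohort. SAP 8.3.5, the section on laboratory data, says only: "Laboratory data will be listed in accordance with the sponsor reporting standards". For vital signs, SAP 8.3.6 defines baseline, calls for descriptive statistics of baseline and change within each cohort, and adds a listing.

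**The concern.** Two sections of the SAP (6.2 and the 8.3 lead-in) point to laboratory summaries, and the section that should specify them plans a listing. A programmer working from 8.3.5 would produce no laboratory table. A programmer working from 6.2 would have to invent one, with no baseline rule, no change statistic and no abnormality criterion to follow.

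At stake is the cohort-level description of laboratory safety in a trial that the sponsor labels a post-authorization safety study and that has no data monitoring committee (Protocol 9.7). A reader of the report would have to work child by child through listed values, over an age span of 1 to 16 years, to learn whether an analyte such as ALT, magnesium, creatine kinase or gastrin moved during treatment.

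**Working it through.** The plan gives no figure on this point, so the check is to set the texts side by side.

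**1. Assessments named in Protocol 2.2.2 against SAP outputs**

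| Assessment | In SAP 6.2 list | Summary specified in SAP 8.3.x | Listing specified in SAP 8.3.x |
|---|---|---|---|
| Adverse events | yes | reported by cohort under sponsor standards (8.3.4) | left to sponsor standards |
| Blood pressure and pulse rate | yes, as vital signs | baseline and change by cohort (8.3.6) | yes (8.3.6) |
| Laboratory measurements | yes | none | yes (8.3.5) |
| Physical examination | no | none | none |

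Blood pressure and pulse rate share a row, so the four rows cover the five named assessments. SAP 8.3.2 mentions clinical examination in its heading, but its content is age, race, weight, body mass index and height.

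**2. Does listing imply summarising in this SAP?** No. Sections 8.3.6 and 8.3.7 each ask for a summary and then, in a separate sentence, for a listing. Sections 8.3.8 and 8.3.9 ask for listings only. By that usage 8.3.5 plans a listing and no table. SAP 8.3.1 nevertheless counts children analysed for laboratory data, although no analysis of those data is defined.

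**3. Does adverse event reporting fill the gap?** In part. Under Protocol 8.5 an abnormal result is reported as an adverse event if it comes with symptoms, needs further testing or intervention, changes study dosing or other treatment, or is judged to be an event. Protocol 8.6.2 makes potential Hy's law cases serious adverse events. Abnormalities of that kind reach the by-cohort adverse event output. Other shifts out of range, and central values, do not.

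**4. Why the missing baseline rule matters.** Inclusion criterion 5 admits children with out-of-range laboratory values if the investigator documents that these are not clinically significant or relate to the underlying condition. A post-treatment abnormality is therefore hard to read without the child's own starting value. Screening values may come from tests up to 1 week before dosing (Protocol 6.1), and final values from routine tests within 48 hours after the last dose (Protocol 7.5). SAP 8.3.6 defines baseline for vital signs only.

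**5. Volume of data affected.** Counting Protocol Table 1, with red cell indices separate and a five-part white cell differential assumed: 13 haematology + 16 chemistry + 1 gastrin = 30 blood analytes. Then 30 analytes × 2 time points × 24 children = 1,440 values, before urinalysis. This measures volume; it is not a measure of bias or harm.

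**6. What cohort counts could show.** If 0 of 12 children in a cohort have a new abnormality, the exact upper limit is 1 − 0.05^(1/12) = 22.1% one-sided at 95%, or 1 − 0.025^(1/12) = 26.5% for a two-sided 95% interval. With cohorts this small, counts describe what was seen and exclude only large rates.

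**The case against.** The strongest reply is that the SAP does not abandon laboratory summaries. Section 6.2 and the opening of 8.3 both point to them, Protocol 9.5 ties safety summaries to CDISC and sponsor standards, and those standards may contain default laboratory tables or listings with range flags. They are not among the documents, so this can be neither confirmed nor excluded. It remains that 8.3.5 invokes the standards for a listing only, and that the other places specify no table.

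The protocol's commitment is also softer than a quick reading suggests. The sentence that says laboratory data are summarised concerns ongoing review during the study, and the presentation sentence is limited to where it is appropriate. That stands: a final table for each assessment is not promised without condition. The sentence on describing laboratory abnormalities carries no such limit, however, and the SAP is the place to settle what is appropriate.

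A reader might infer that two safety endpoints are left without any result. The documents do not support that. Laboratory tests and physical examinations are two of five means of assessing one endpoint. A listing is an output, and clinically relevant changes can reach the adverse event tables: Protocol 8.3 gives changes in examination findings as an example of an adverse event. Only physical examination has no named SAP output, and that is mainly missing detail.

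Finally, exact intervals for each analyte would be a matter of preference in a study that SAP 8.1 calls descriptive. That also stands.

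**Conclusion.** The concern holds as an inconsistency. SAP 8.3.5 conflicts with SAP 6.2, with the SAP 8.3 lead-in and with Protocol 9.5. Followed literally, it leaves laboratory measurements without a by-cohort summary, apart from abnormalities that qualify as adverse events. The size is moderate to low: safety is a secondary objective, there are about 12 children per cohort, the values will be collected and listed in any case, and the primary pharmacokinetic endpoints are untouched. It should still be corrected, because the change is cheap and makes the laboratory part of the safety endpoint reportable by cohort.

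This rests on reading 8.3.5 by the SAP's own distinction between summaries and listings, and on the sponsor standards not overriding it, which cannot be checked here.

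**What to change.** Amend SAP 8.3.5 so that it agrees with 6.2 and 8.3:

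- define the laboratory baseline as the last value before the first dose;
- for each analyte in Protocol Table 1 measured on a numerical scale, including gastrin and magnesium, give by cohort the descriptive statistics of baseline, end-of-treatment value and change;
- by cohort, count the children who shift from normal at baseline to above or below the reporting laboratory's age-specific range, with the number normal at baseline as denominator;
- state or reference the criteria for the abnormalities that Protocol 9.5 says will be described;
- keep the listing.

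Exact intervals for the counts are optional. In Cohort 2, with ages from 2 to 16 years, the shift counts will be easier to interpret than means of raw values, because they use age-specific ranges.

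As a secondary clarification, add one line saying whether physical examination findings are listed, tabulated against screening, or reported through adverse events only.

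The cost is SAP text and two or three extra standard tables, from data already collected and with no added burden on the children. The downside is small cell counts.

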8.3.6. Vital Signs Data

The baseline measurement is the last predose measurement.

For each planned timepoint, baseline values and change from baseline values within each cohort will be summarized with descriptive statistics (using sponsor default standards).

These data will be listed in accordance with the sponsor reporting standards.

8.3.7. Other Safety Data

Primary diagnosis, including method of diagnostic confirmation, will be summary tabulated by cohort. These data will be listed in accordance with the sponsor reporting standards.

8.3.8. Concomitant Treatments

All concomitant medication(s) as well as non-drug treatment(s) will be provided in the listings.

8.3.9. Screening and Other Special Purpose Data

- CYP2C19 genotyping data will be listed in accordance with the sponsor reporting standards.
- Serum B-hCG for all females of childbearing potential will be obtained at Screening. These data will not be brought in-house, and therefore will not be listed.

9. REFERENCES

None.

10. APPENDICES

Appendix 1. SAS CODE FOR ANALYSES

Not applicable.
